Subsequent infusions: If the first infusion of obinutuzumab was well tolerated (defined by an absence of IRRs during a final infusion rate of ≥ 100 mg/hr), subsequent infusions will be administered at an initial rate of 100 mg/hr. The infusion rate may be increased by 100 mg/hr increments at 30-minute intervals, as tolerated, to a maximum rate of 400 mg/hr. Alternatively, if an IRR was present during the first infusion, the administration may be per the guidance from the first infusion with a maximum rate that which has been previously tolerated by the subject. At the investigator's discretion, obinutuzumab infusions may be split and administered over 2 days.

	Dose of Obinutuzumab	Rate of Infusion (in the absence of infusion reactions/hypersensitivity during previous infusions)
Day 1	100 mg	Administer at 25 mg/hr over 4 hours. Do not increase the infusion rate.
Day 1 or 2	900 mg	Administer at 50 mg/hr. The rate of the infusion can be escalated in increments of 50 mg/hr every 30 minutes to a maximum rate of 400 mg/hr.
Subsequent	1000 mg	Infusions can be started at a rate of 100 mg/hr and increased by 100 mg/hr increments every 30 minutes to a maximum of 400 mg/hr.

Management of infusion-related reactions (IRRs)

In case of IRR, the following measures should be considered depending on the severity of the IRR:

- Acetaminophen/paracetamol 1000 mg if not administered during the last 4 hrs
- Antihistamines including a H1- (eg, dimetindene 4 mg IV) and a H2-antagonist (eg, ranitidine 50 mg IV) if not administered during the last 4 hours
- Prednisolone or prednisone 100 mg IV in case of urticarial, bronchospasm and dyspnea
- Intravenous fluids
- Bronchodilators and oxygen in case of bronchospasm and dyspnea
- Vasopressors in case of hypotension

Once symptoms have resolved completely, obinutuzumab may be resumed at 50% of the infusion-rate used prior to the interruption. If no infusion related symptoms occur, the rate of the infusion may be escalated stepwise with 50 mg/hr every 30 minutes to a maximum rate of 400 mg/hr, except for the first administration of obinutuzumab. The first obinutuzumab administration (100 mg) may be re-started at half initial rate (12.5 mg/hr) upon complete resolution of symptoms; if this is tolerated well for an hour, the rate may be increased to a maximum of 25 mg/hr.

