It needs to be stressed that in the event of a life-threatening (which may include pulmonary or cardiac events), prolonged or recurrent IRR, obinutuzumab should be discontinued immediately and no further obinutuzumab should be administered.

Patients experiencing Grade 3 or 4 IRRs twice should receive aggressive symptomatic treatment and will be discontinued from further study treatment with obinutuzumab. Treatment with oral agents should be continued with the subject remaining on study.

For guidance on the management of infusion-related reactions (IRRs) see the following table:

IRR Severity (NCI CTCAE v4.0)	Recommendation
Grade 1-2	Reduce the infusion rate or hold infusion Administer supportive treatment Upon symptom resolution, restart infusion at no more than half the previous rate (the rate being used at the time that the IRR occurred) and, if patient does not experience any IRR symptoms, infusion rate escalation may resume at the increments and intervals as appropriate for the treatment dose
Grade 3	Discontinue infusion immediately Administer supportive treatment Upon symptom resolution, may resume infusion rate escalation, at the investigator's discretion Treatment must be permanently discontinued, if same adverse event recurs with same severity.
Grade 4	Discontinue infusion immediately Treat symptoms aggressively Do not restart obinutuzumab

Reductions in obinutuzumab dosing are not planned. Repeat obinutuzumab administrations may be delayed to allow subjects to recover from obinutuzumab-related AEs or intercurrent illness.

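### Protocol Section 5.3.2 bars further obinutuzumab after any prolonged or recurrent infusion-related reaction, while its severity table directs or allows continuation in the same cases

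*Protocol*

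**What the plan says.** All the text is in Protocol Section 5.3.2. The letters are labels for use below.

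- **Paragraph A.** After naming life-threatening reactions, the sentence continues: "prolonged or recurrent IRR, obinutuzumab should be discontinued immediately and no further obinutuzumab should be administered". Neither *prolonged* nor *recurrent* has a grade or a definition.
- **Paragraph B**, which follows: "Patients experiencing Grade 3 or 4 IRRs twice should receive aggressive symptomatic treatment and will be discontinued from further study treatment with obinutuzumab".
- **Table C**, by severity. Grade 1-2: "Upon symptom resolution, restart infusion at no more than half the previous rate", with no limit on how often. Grade 3: "Upon symptom resolution, may resume infusion rate escalation", at the investigator's discretion, and then: "Treatment must be permanently discontinued, if same adverse event recurs with same severity". Grade 4: "Do not restart obinutuzumab".
- **Resumption text D**, earlier in the section and without a grade: "Once symptoms have resolved completely, obinutuzumab may be resumed at 50% of the infusion-rate used prior to the interruption".

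Two other parts of the section foresee more dosing after an IRR. The premedication text for later infusions provides for a corticosteroid when the previous infusion produced a Grade 3 IRR. The text on subsequent infusion rates says that "if an IRR was present during the first infusion, the administration may be per the guidance from the first infusion". Nothing in the section states which instruction takes precedence.

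**The concern.** Paragraph A is a stopping rule without a grade. Table C is graded, and it directs or permits continuation in situations that A covers. Two sites with identical subjects could each follow the protocol and do opposite things.

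Two things are at stake. The first is subject safety, because the conflict concerns whether a subject who has reacted is exposed again. The second is exposure to obinutuzumab, planned as 8 doses over 21 weeks. It is the component that distinguishes Arm B. Section 1.5 explains that Arm B was kept, and Arm A closed, after 0 of 10 evaluable CLL subjects reached CR on the doublet in the Phase 1b study. A subject who stops obinutuzumab stays on the oral agents and remains in the Full Analysis Set for the Week 25 CR rate. The SAP also reports obinutuzumab completion status with reasons (Section 4.1), number of infusions (Section 4.2.1) and adverse events leading to its discontinuation (Section 7.1.6.1). These summaries are hard to interpret if sites apply different rules.

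**Working it through.** There is no plan figure to reproduce. The check applies each instruction to the same hypothetical subject.

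| Subject | Paragraph A | Paragraph B | Table C | Result |
|---|---|---|---|---|
| First, brief Grade 1-2 IRR | not triggered | not triggered | restart | agree |
| Second Grade 1-2 IRR | stop (recurrent) | not triggered | restart | conflict |
| Grade 3 IRR after an earlier Grade 1-2 IRR | stop (recurrent) | not triggered | may resume | conflict |
| First Grade 3 IRR, prolonged | stop (prolonged) | not triggered | may resume once resolved | conflict |
| Two Grade 3 IRRs, different manifestations | stop | stop | stop condition not met; may resume | conflict |
| Same Grade 3 event twice | stop | stop | stop | agree |
| Single Grade 4 IRR | stop (life-threatening) | not triggered | do not restart | agree |

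**Kind of conflict.** For a second Grade 1-2 IRR, A and C cannot both be followed: one bars further drug and the other directs a restart. For the Grade 3 rows, C gives discretion where A, and in the last of them also B, orders a stop. A site could satisfy both by declining to resume, but the table tells it that resuming is allowed.

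**Dependence on reading.** The row with two different Grade 3 manifestations conflicts if the adverse event in the Grade 3 row means the manifestation. If it means the IRR itself, that row agrees. The text does not say which is meant.

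**Grade 4.** Section 7.2.2 and Table 7-1 grade life-threatening events as 4, so A and the Grade 4 row both stop after one event. B is awkward beside them, because two Grade 4 IRRs presuppose re-exposure after the first. Text D, having no grade, does not exclude Grade 4 either.

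**Scale.** Inputs are about 30 Arm B subjects (Section 8.9) and the two sets of IRR rates in Section 1.4. These are 65% any grade and 20% Grade 3/4 in the obinutuzumab plus chlorambucil trial, and 19% any grade and 9% Grade 3 or higher in the idelalisib plus obinutuzumab study. Expected number = 30 × rate.

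- Any grade: 30 × 0.65 = 19.5 and 30 × 0.19 = 5.7, so about 6 to 20.
- Grade 3 or higher: 30 × 0.20 = 6 and 30 × 0.09 = 2.7, so about 3 to 6.

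These count everyone with an IRR. The conflicting rows need a repeat IRR or a prolonged one, and the documents give a rate for neither.

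**The case against.** **The rules may be cumulative.** Each stopping sentence can be read as sufficient by itself, so that a site stops whenever any one applies. This is the best defence, and it settles Grade 4. It does not settle the rest, because the protocol never states it and the table affirmatively directs a restart where A bars further drug.

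**Emphasis and flexibility.** A is introduced as a point to be stressed, whereas the table is offered as guidance under a column of recommendations. That hints that A prevails, but it is not a precedence clause, and the table's own Grade 3 row uses mandatory language. The clause in Section 6.5 that allows investigators to depart from the guidelines names Tables 6-2 and 6-3, not this table.

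**The Grade 1-2 row may concern only the infusion in progress.** It is indeed silent on recurrence across infusions, and the subsequent-infusion text quoted above addresses a reaction at the first infusion, not a second one. But the conflict arises within a single infusion too. If a second mild reaction occurs at Week 2, the row says to restart that infusion and A says to end the drug at once.

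**A stronger reading.** A reader might infer from B that obinutuzumab may be given again after one Grade 4 IRR. The documents do not support this. B says what happens after two such events and does not say that only two will do. It is silent on one, and the two instructions that address one both stop. What stands is a mismatch of wording.

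**Effect on CR.** An effect on the Week 25 CR rate is plausible but not shown. No document gives a relation between infusions received and CR.

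**Conclusion.** The point holds. Section 5.3.2 gives conflicting instructions for a second Grade 1-2 IRR, a Grade 3 IRR after a milder one, a prolonged first Grade 3 IRR and, on one reading of the table, two Grade 3 IRRs with different manifestations. For a single Grade 4 IRR the stopping instructions agree, and only paragraph B's wording needs alignment.

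The number of subjects affected cannot be derived. A reader might take 6 to 20, or 3 to 6, as that number. They are ceilings on subjects with any IRR and with a Grade 3 or higher IRR. They assume that rates from previously untreated CLL carry over to relapsed or refractory disease. Section 1.4 also notes that most IRRs came with the first infusion and that splitting the first dose helped in part, so the number with a repeat reaction is probably smaller.

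Sample size and confidence-interval precision are unaffected. The point still has to be resolved, because a stopping rule that bears on safety should not depend on which paragraph a site reads, and about 25 centers are planned.

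**What to change.** Reconcile paragraphs A and B, the severity table and the ungraded resumption text into one rule set, arranged by grade and by first or repeat event. It should state:

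- for each grade, whether a first event, a repeat at the same grade and a repeat at a different grade ends obinutuzumab;
- what *recurrent* and *prolonged* mean, with a grade attached, and whether recurrence is counted within an infusion, across infusions or both;
- whether the adverse event in the Grade 3 row is the IRR or its manifestation;
- how paragraph B and the resumption text apply to Grade 4, so that they match the Grade 4 row and the life-threatening clause.

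Remove the sentences that then disagree, or make them expressly subordinate, and check the premedication and subsequent-infusion text against the result. Which clinical rule holds is the sponsor's choice; this review takes no view. The cost is protocol wording and a letter to sites, with no added visits or procedures.

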5.4. Prior and Concomitant Medications

Subjects must not have previously progressed on treatment with inhibitors of BTK, SYK, PI3K, BCL-2 or obinutuzumab.

Subjects should not have had treatment or prophylaxis for CMV within 28 days of starting therapy with idelalisib or obinutuzumab.

Subjects should not be treated with a strong CYP3A4 or a strong P-gp inducer within 2 weeks of study treatment initiation; if chronic administration of such an agent is needed after study initiation, this situation should be immediately discussed with the study medical monitor.

5.4.1. ***Pneumocystis (carinii) jirovecii* Pneumonia Prophylaxis**

Subjects must receive trimethoprim-sulfamethoxazole or other established prophylaxis for PJP throughout the course of idelalisib treatment. Prophylaxis should continue for a period of 2 to 6 months after the last dose of idelalisib. The duration of prophylaxis should be based on clinical judgment of the investigator and may take into account risk factors such as concomitant corticosteroid treatment and prolonged neutropenia after idelalisib treatment ends.

Immunization with live or attenuated viral vaccines is not recommended while on treatment during this study.

5.4.2. **IVIg and G-CSF**

Administration of IVIg or G-CSF is permitted per institutional standard of care.

5.4.3. **Prior and Concomitant Medications with Tirabrutinib**

In vitro data indicate tirabrutinib is a substrate of CYP3A4 and P-gp. Co-administration of CYP3A4 inhibitors may increase tirabrutinib exposure. However, preliminary PK data from study GS-US-401-1757 indicate idelalisib, a CYP3A4 inhibitor, does not cause a clinically relevant increase in tirabrutinib exposure indicating tirabrutinib is not a sensitive CYP3A4 substrate. As such, co-administration of strong CYP3A4 inhibitors with study drug is allowed in this study, but caution should be exercised. Co-administration of the strong CYP3A4 and P-gp inducer, rifampin, resulted in a significant decrease in tirabrutinib exposure (~70%). As such, potent CYP3A4 or P-gp inducers are prohibited while subjects are on study drug and within 2 weeks prior to study drug administration. Examples of strong CYP3A4 or P-gp inducers are provided in the table below.

In vitro data indicate tirabrutinib has the potential to inhibit several CYPs and transporters. Therefore, tirabrutinib may affect the plasma concentrations of their substrates. Caution should be exercised when co-administering concomitant medications that are metabolized by CYP3A4/5 and transported by OAT3, OATP1B1, MATE1, OCT1, OCT2, or P-gp.

Table 5-1. Examples of Concomitant Medications Prohibited in this Study

	Strong
CYP3A4/P-gp Inducer	carbamazepine, phenytoin, rifampin, St. John's Wort, enzalutamide

5.4.4. Prior and Concomitant Medications with Idelalisib

The major metabolite of idelalisib, GS-563117, is a competitive and time dependent inhibitor of CYP3A; accordingly coadministration of idelalisib 150 mg twice daily with midazolam, a probe CYP3A substrate, resulted in an approximately 5-fold increase in midazolam systemic exposure (AUC). At the planned dose of idelalisib in this study (100 mg once daily), idelalisib is predicted to be a moderate CYP3A4 inhibitor. Coadministration of CYP3A substrates with idelalisib may result in an increase in their systemic exposures (eg, certain antiarrhythmics, calcium channel blockers, benzodiazepines, HMG-CoA reductase inhibitors, phosphodiesterase-5 (PDE5) inhibitors, and warfarin, see [Table 5-1](#)). Particular caution is recommended during coadministration of idelalisib with drugs that are highly dependent on CYP3A for clearance and for which elevated plasma concentrations are associated with serious and/or life-threatening events, including narrow therapeutic index CYP3A substrates (eg, alfentanil, cyclosporine, sirolimus, tacrolimus, cisapride, pimozide, fentanyl, quinidine, ergotamine, dihydroergotamine, astemizole, terfenadine see [Table 5-1](#)) with idelalisib. The investigator should review the prescribing information of the concomitant medication for guidance on coadministration with a CYP3A inhibitor.

5.4.5. Prior and Concomitant Medications with Obinutuzumab

In accordance with current obinutuzumab prescribing information, subjects should be premedicated with an antipyretic and an antihistamine to reduce the incidence and severity of infusion reactions. A recommended regimen is diphenhydramine, 25 to 50 mg orally, and acetaminophen (paracetamol) 650 to 1000 mg orally, both given approximately 30 minutes prior to each obinutuzumab administration. In addition, an intravenous corticosteroid should also be administered as a premedication on Days 1, 2, 8, and 15 for all subjects, completed at least 1 hour prior to administration of obinutuzumab, and then only as indicated per the prescribing information. Local practices and guidelines may be followed.

5.4.5.1. Tumor Lysis Syndrome

Subjects with a high tumor burden ($WBC \geq 25 \times 10^9/L$ or bulky lymphadenopathy) must receive prophylaxis for tumor lysis syndrome (TLS) prior to the initiation of treatment. Prophylaxis for subjects with renal impairment ($CrCl < 70\text{mL}/\text{min}$) should also be considered. Subjects must be well hydrated. It is desirable to maintain a fluid intake of approximately 3 liters per day, 1-2 days before the first dose of obinutuzumab. All subjects with high tumor burden must be treated with allopurinol (≥ 300 mg p.o./day) or a suitable alternative treatment (eg, rasburicase) starting 12-24 hours prior to the first infusion. Subjects should continue to receive repeated prophylaxis with allopurinol and adequate hydration prior to each subsequent infusion, if deemed appropriate by the investigator. Older and frail subjects will need special individualized care in fluid management, as 3 liters per day may not be tolerated. Rasburicase may be particularly indicated in such subjects. For all subjects, electrolytes should be monitored and corrected, fluid balance and renal function should be monitored, and supportive care should be administered, including dialysis as indicated. Hospitalization, particularly for older and frail subjects, should be considered.

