In a Phase 3 trial, patients were treated with chlorambucil alone, GAZYVARO in combination with chlorambucil, or rituximab product in combination with chlorambucil. The Stage 1 analysis compared GAZYVARO in combination with chlorambucil vs. chlorambucil alone, and Stage 2 compared GAZYVARO in combination with chlorambucil vs. rituximab product in combination with chlorambucil.

The most common Grade 3 to 4 adverse reactions (incidence $\geq 10\%$) observed in patients with CLL in the GAZYVARO containing arm of clinical trials were neutropenia, infusion reactions, and thrombocytopenia.

The most common adverse reactions (incidence $\geq 10\%$) observed in patients with CLL in the GAZYVARO containing arm were infusion reactions, neutropenia, thrombocytopenia, anemia, pyrexia, cough, nausea, and diarrhea.

The most common obinutuzumab-related events are infusion-related reactions and tumor lysis syndrome, most commonly during the initial administration, hypersensitivity (immediate or delayed onset), and worsening of pre-existing cardiac conditions. Some patients receiving obinutuzumab have experienced cytopenias or infections. Obinutuzumab use has been associated with hepatitis B virus (HBV) reactivation and very rare cases of progressive multifocal leukoencephalopathy. Mitigation strategies are defined in this protocol. To reduce the incidence and severity of obinutuzumab-related infusion reactions, established premedication regimens and infusion modification algorithms have been included (Section 5.3.2). To mitigate the risk of *Pneumocystis jirovecii* pneumonia, antibiotic prophylaxis is required (Section 5.4.1).

To mitigate the risk of HBV reactivation in subjects treated with an anti-CD20 antibody, HBV screening will be performed. Subjects who are hepatitis B core antibody positive at screening may be enrolled only if the plasma DNA PCR test is negative, and will be monitored for potential HBV reactivation (manifested as detectable HBV DNA by quantitative PCR). Subjects will be tested monthly for the duration of obinutuzumab therapy and every 3 months thereafter for 1 year from the last dose of obinutuzumab therapy in this study. Specific instructions for supportive care in response to myelosuppression are described. Investigators are instructed to institute prophylaxis and monitoring for tumor lysis syndrome for subjects with a high tumor burden, high circulating lymphocyte count ($>25 \times 10^9/L$) or renal impairment ($CrCl < 70 mL/min$).

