Patients with a high tumor burden (leukocyte counts $\geq 25 \times 10^9/L$ and/ or bulky lymphadenopathy) and/or renal impairment ($CrCl < 70$ mL/min) are at risk for developing a tumor-lysis syndrome (TLS). These patients with a high tumor burden and also all other patients considered at risk for TLS by the investigator must receive prophylaxis for TLS prior to the initiation of treatment with obinutuzumab and ahead of all subsequent administrations of obinutuzumab until the tumor burden is reduced and risk for development of a TLS is minimized. Possible preventive measures include:

- adequate hydration (eg, intravenous administration of 1000 – 4000 mL NaCl 0.9% starting 12 – 24 hours before treatment),
- prophylactic administration of an uric acid reducer (eg, allopurinol 300 mg once daily starting 12 – 24 hours prior to initiation of treatment) and/or
- rasburicase (*Fasturtec*[®]).

In addition, a close monitoring of serum chemistry, particularly creatinine, potassium and uric acid levels must be performed. Patients with TLS should be treated per institutional practice (including correction of electrolyte abnormalities, monitoring of renal function and fluid balance, administration of supportive care, including dialysis as indicated).

Infusion Rates

First infusion: All subjects will receive an infusion of the fixed dose of 100 mg obinutuzumab administered at a fixed rate of 25 mg/hr over 4 hours. If the first 100 mg obinutuzumab is tolerated well and completed without interruptions or adjustments of infusion rate and it is possible from an organizational and medical point of view (enough time, medical supervision available throughout the infusion), patients are allowed to continue with the remaining 900 mg infusion on the same day. Otherwise the remaining 900 mg should be infused the next day. The infusion with 900 mg obinutuzumab should be started at a rate of 50 mg/hr in all patients and the infusion rate may be escalated in increments of 50 mg/hr every 30 minutes to a maximum rate of 400 mg/hr.

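### The protocol's three passages on tumor lysis prophylaxis disagree on initial prophylaxis in renal impairment and on repeat prophylaxis before later obinutuzumab infusions

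*Protocol*

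**What the plan says.** Three places in the current protocol text address TLS prophylaxis around obinutuzumab.

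- **Section 1.6 (Risk/Benefit Assessment).** TLS is listed among the most common obinutuzumab-related events, and the section states that the protocol defines mitigations. One of them reads: "Investigators are instructed to institute prophylaxis and monitoring for tumor lysis syndrome for subjects with a high tumor burden". The same sentence adds a high lymphocyte count "or renal impairment", defined as CrCl below 70 mL/min, as further triggers. It does not soften the instruction for any of them and says nothing about later infusions.
- **Section 5.3.2 (Obinutuzumab).** Patients with high tumor burden and/or CrCl below 70 mL/min are named as at risk. The requirement follows in a separate sentence: "These patients with a high tumor burden and also all other patients considered at risk for TLS by the investigator must receive prophylaxis". It also applies before every later infusion, "until the tumor burden is reduced and risk for development of a TLS is minimized".
- **Section 5.4.5.1 (Tumor Lysis Syndrome).** Prophylaxis before treatment is compulsory for high tumor burden. A separate sentence, beginning "Prophylaxis for subjects with renal impairment" and using the same 70 mL/min threshold, asks only that it be considered. Continued prophylaxis is worded as a *should*, "prior to each subsequent infusion, if deemed appropriate by the investigator".

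**The concern.** Section 1.6 is where an ethics committee or regulator reads how a known serious risk is controlled. If a dosing or medication section is weaker than that description, the control described may not be the control delivered.

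Conduct is affected too. If prophylaxis is omitted in a renally impaired subject, or not repeated in a high-burden subject, monitors cannot say consistently whether the protocol was breached. Two sites could act differently and each point to a section that supports them. SAP Section 4.3 tabulates important protocol deviations, so the same event could be counted at one site and not at another.

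**Working it through.** No arithmetic underlies the point itself. The check is to set the three sections side by side and then establish who can be affected.

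**Step 1. Strength of instruction by group and time.**

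| Protocol section | First infusion, high tumor burden | First infusion, CrCl < 70 mL/min without high tumor burden | Later infusions |
|---|---|---|---|
| 1.6 | Instructed | Instructed | Not addressed |
| 5.3.2 | Must | Named as at risk; *must* applies if the investigator considers the patient at risk | Must, until burden is reduced and risk minimized |
| 5.4.5.1 | Must | To be considered | Should, if the investigator finds it appropriate |

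The first column is consistent. The other two are not.

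**Step 2. Renal impairment.** The clear conflict is Section 1.6 against Section 5.4.5.1: same group, same threshold, an instruction in one and a consideration in the other. Within Section 5.4.5.1 the weaker wording comes directly after a *must* for high tumor burden, so it reads as a deliberate lower tier. Section 5.3.2 is a third, intermediate wording. Its risk sentence includes renal impairment, but its *must* sentence does not repeat it.

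**Step 3. Repeat prophylaxis.** Section 5.3.2 says the patients it covers "must receive prophylaxis for TLS prior to the initiation of treatment with obinutuzumab and ahead of all subsequent administrations of obinutuzumab". Until its end condition is met, that is compulsory. Section 5.4.5.1 leaves each repeat to the investigator from the outset.

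**Step 4. Who is affected.**

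- Inclusion criterion 4 requires CrCl of at least 50 mL/min and the TLS threshold is 70 mL/min, so subjects from 50 to below 70 mL/min can be enrolled.
- Arm A (approximately 6 subjects) receives no obinutuzumab. Of approximately 36 subjects, 36 − 6 = 30 are in Arm B.
- Conflict on initial prophylaxis: Arm B subjects with CrCl 50 to below 70 mL/min and no high tumor burden. The documents give no share, so the planned numbers bound this only between 0 and 30.
- Conflict on repeat prophylaxis: all at-risk Arm B subjects, including those with high tumor burden. Obinutuzumab is given as 8 doses, so up to 8 − 1 = 7 later infusions per subject fall under the two wordings.

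**The case against.** The best case for the protocol is that its two operative sections can be read together on renal impairment. On its literal wording, Section 5.3.2 leaves a patient with CrCl below 70 mL/min and no high tumor burden to the investigator's view of risk, which is compatible with considering prophylaxis under Section 5.4.5.1. The firm contrary wording is then one sentence in a risk/benefit narrative, which might be called a loose summary. The repeat requirement in Section 5.3.2 also ends on a clinical judgement with no stated threshold, so both sections depend on the investigator's assessment of continuing risk.

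Much of this stands, and it limits what can be claimed:

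- A reader might infer that Section 5.3.2 makes prophylaxis compulsory for everyone with CrCl below 70 mL/min. Its *must* sentence does not say so.
- A reader might infer that a site following Section 5.4.5.1 would leave renally impaired subjects without protection. That section also requires subjects to be well hydrated, without limiting this to high tumor burden, and calls for monitoring of electrolytes, fluid balance and renal function in all subjects. What is left open for this group is mainly the uric-acid-lowering drug.
- A reader might infer that every subject with CrCl 50 to below 70 mL/min is affected by the first conflict. Those with high tumor burden must receive initial prophylaxis under both operative sections, and Arm A is outside these instructions.

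The objection does not remove the conflicts. Even a loose summary in Section 1.6 describes a stronger control than Section 5.4.5.1 provides. Until its end condition is reached, the repeat requirement in Section 5.3.2 is a *must*, whereas Section 5.4.5.1 makes every repeat discretionary. No other text resolves this. The allowance for local practice in Section 5.4.5 closes a paragraph on infusion premedication, and the latitude in Section 6.5 covers Tables 6-2 and 6-3. Nothing states which section prevails.

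**Conclusion.** The point holds as an internal inconsistency in two respects.

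1. **Initial prophylaxis in renal impairment.** Section 1.6 conflicts with Section 5.4.5.1, with Section 5.3.2 in between. A site following Section 5.4.5.1 *could* omit prophylaxis that Section 1.6 presents as a mitigation; the text does not show that it *would*.
2. **Repeat prophylaxis.** Section 5.3.2 conflicts with Section 5.4.5.1 for all at-risk Arm B subjects. This is the broader of the two because it includes subjects with high tumor burden whatever their renal function.

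The number affected cannot be derived from the documents. The conclusion rests on the literal wording of the *must* sentence in Section 5.3.2 and on these instructions applying only where obinutuzumab is given. It takes no view on which rule is clinically right. The CR endpoint, its confidence interval and the sample size are untouched. This is a matter of safety conduct and consistency that should be corrected.

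**What to change.** Reconcile Sections 1.6, 5.3.2 and 5.4.5.1 into one statement, held in one place and cross-referenced from the others. It should cover four cells: initial and repeat prophylaxis, each for the high-tumor-burden group and for the renal-impairment group. For each cell it should say whether prophylaxis is required or left to the investigator, and, where a repeat requirement ends, what ends it. Limiting the correction to renal impairment would leave most of the repeat conflict in place. The sponsor must decide which rule applies.

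The cost is a protocol clarification and notice to sites. No change to the SAP, the analysis or the sample size is needed.
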